3.2 Background

Acute Myeloid Leukemia

Leukemia is a neoplastic proliferation of hematopoietic cells. These cells are either at undifferentiated or partially differentiated stages of maturation. As a consequence of excessive proliferation of the immature precursors, these cells eventually replace the normal blood-forming elements of the bone marrow, resulting in neutropenia, anemia, and thrombocytopenia. Acute myeloid leukemia (AML) can occur at any age and accounts for one-third of the leukemias diagnosed in patients >20 years. Incidence increases with age, with the median age at time of diagnosis around 68 years and the median age at time of death around 72 years^{3 4}. In individuals \geq 65 years, the incidence of AML is almost 10 times higher than in those < 65 years (17 per 100,000 versus 1.8 per 100,000, respectively)⁵. In Japan, the number of AML patients is estimated to be about 7,000 in 2017⁶. The incidence of AML in Japan is estimated to be 2 to 3 per 100,000, and the incidence increases with age in Japan as in the US.⁷

Two classification systems have been used for defining AML. In the classic French-American-British (FAB) system, morphology (based primarily on cytochemistry) defines the level of maturation and differentiation of the blasts; the threshold between myelodysplasia and AML is arbitrarily drawn at 30% blasts. Eight subtypes of AML have been described and are named according to the involved cell type. The more recent World Health Organization (WHO) classification seeks to further refine differences in leukemia biology by incorporating cytogenetic information, prior history of myelodysplasia, or therapy with certain chemotherapy agents or radiation therapy and presence of dysplasia⁸.

More recently, the prognostic risk in AML is determined not only by cytogenetic abnormalities, (ie, chromosomal deletions, duplications, or translocations) but also by several somatic molecular alterations (gene mutations)². The molecular genetic landscape of AML is complex, and several genes like CEBPA, NPM1, FLT3, RUNX1, P53, and ASXL1 are now part of risk assessments of AML patients. The current European LeukemiaNet (ELN) favorable risk criteria include t(8;21)(q22;q22.1); RUNX1-RUNX1T1; inv(16)(p13.1q22) or t(16;16)(p13.1;q22); CBFB-MYH11. Normal cytogenetics portends intermediate-risk AML. AML that is often characterized

by deletions of the long arms (monosomies) of chromosomes 5 or 7; by translocations or inversions of chromosome 3, t(6;9), t(9;22); or by abnormalities of chromosome 11q23 have particularly poor prognoses with chemotherapy. Acute myeloid leukemia may also arise secondary to previous cytotoxic chemotherapy or arise through transformation from existing myelodysplasia. Therapy-related AML arising from exposure to environmental toxins, cytotoxic drugs, or radiation currently accounts for about 10% to 30% of all cases of AML⁹. It is estimated that 35% to 40% of patients with myelodysplastic syndromes (MDS) will develop AML, with the disease often refractory to current therapy¹⁰.

Current AML Treatments

The standard treatment modality for AML is chemotherapy globally, including in Japan. The therapeutic approaches are usually divided into two phases: induction of remission and post-remission (consolidation) therapy. For more than 30 years, the combination of cytarabine and an anthracycline has been the mainstay of treatments to induce remission^{11 12}. The induction of remission therapy in leukemia is designed to produce rapid restoration of normal bone marrow function. A common induction regimen consists of cytarabine 100 mg/m²/day for 7 days combined with daunorubicin 60 to 90 mg/m²/day for 3 days, often referred to as the “7+3 protocol.” With the combination of cytarabine and daunorubicin or their analogues, a CR, conventionally defined by the presence of < 5% blasts in the bone marrow together with recovery of peripheral-blood absolute neutrophil and platelet counts, can be achieved in up to 60% to 80% of adults with de novo AML who are < 60 years^{11 12}. If CR is achieved, there are three basic treatment choices for post-remission therapy: additional chemotherapy, stem cell transplantation from a donor (allogeneic stem cell transplantation), or stem cell transplantation using the patient's own stem cells (autologous stem cell transplantation). For post-remission chemotherapy, the same chemotherapy agent used for remission induction is often repeated for one or more cycles, referred to as consolidation chemotherapy. When several courses of consolidation are given, survival rates at 2 to 3 years are 35% to 50% for young to middle-aged (< 65 years) adults who have achieved CR¹³. However, consolidation or post-remission chemotherapy for elderly (≥ 65 years) patients with AML has not been proven beneficial.

In elderly patients with AML, conventional cytotoxic intensive chemotherapy has been associated with CR rates of approximately 45%, considerably lower than in younger (< 60 years) patients. Unfortunately, the duration of remission is shorter, the early treatment-related mortality is high (approximately 30% to 50%)¹⁴, which in part explains a median survival time between 9 to 12 months^{15 16}. The standard consolidation chemotherapy regimens are not associated with prolonged CR in this elderly age group¹⁷.

When standard chemotherapy (consolidation after remission induction) is given to patients < 65 years, the 5-year survival rate is 48%¹⁸. The 4-year survival rate is reported to be approximately 20% for patients aged 65 to 80 years¹⁹. In Japan, the basic treatment regimen is the same as the above-mentioned treatment regimen outside Japan. For elderly patients, the general conditions and the presence/absence of complications are taken into account when deciding whether induction

therapy should be indicated and when determining the dose of chemotherapy once induction therapy is indicated. If considered to fit the standard treatment, these patients receive induction therapy, as do younger patients. If remission is achieved, patients receive allogeneic HSCT if eligible or consolidation therapy or chemotherapy depending on prognostic factors. If remission cannot be achieved, salvage therapy will be performed²⁰. CC-486 maintenance therapy was added as one option (Category 2B) in the NCCN Clinical Practice Guideline based on the result of the Study CC-486-AML-001²¹; however, maintenance therapy has not been established in Japan²², and until recently, there is no standard for maintenance therapy. Patients who are not candidates for intensive remission induction therapy, such as older adult patients, are treated with low-dose cytarabine, injectable azacitidine with venetoclax, or new drugs^{16 23}.

CC-486 (Oral Azacitidine)

Azacitidine is an analog of the naturally occurring pyrimidine nucleoside cytidine and is classified as an antimetabolite. Vidaza® (injectable azacitidine) is approved by the US Food and Drug Administration (FDA) for the following 5 subtypes of the French-American-British (FAB) classification system of MDS: refractory anemia (RA) or refractory anemia with ringed sideroblasts (RARS) (if accompanied by neutropenia or thrombocytopenia or requiring transfusions), refractory anemia with excess blasts (RAEB), refractory anemia with excess blasts in transformation (RAEB-T), and chronic myelomonocytic leukemia (CMML). Vidaza is also approved by the European Commission for the treatment of adult participants who are not eligible for HSCT with intermediate-2 and high-risk MDS according to the Revised International Prognostic Scoring System (IPSS-R); CMML with 10% to 29% marrow blasts without myeloproliferative disorder; AML with 20% to 30% blasts and multi-lineage dysplasia according to World Health Organization (WHO) classification; and AML with >30% blasts according to WHO classification.

Azacitidine has been extensively studied in MDS and has been shown in a large, randomized Phase 3 trial of higher-risk MDS participants to provide a survival advantage of 9.4 months over conventional care regimens, thus altering the natural course of MDS. The median overall survival (OS) of azacitidine-treated participants was 24.5 months compared with 15.0 months for the combined conventional care regimen group, which included best supportive care (BSC), low-dose cytarabine, and intensive chemotherapy²⁴. Silverman et al²⁵, using WHO AML criteria for diagnosis, reported a median OS of 19.3 months (n=27) in azacitidine-treated participants compared with 12.9 months (n=25) in participants who received BSC. More recently, a multicenter, randomized, Phase 3 study in untreated AML participants reported a CR rate of 27.8% and a clinically meaningful improvement in OS. The median OS was longer for participants treated with azacitidine at 10.4 months compared to those who received conventional care regimens at 6.5 months²⁶. All of the above-mentioned studies used the standard azacitidine dose of 75 mg/m²/day subcutaneous (SC) for 7 days of each 28-day cycle²⁷.

The QUAZAR Study (CC-486-AML-001) has demonstrated that CC-486 maintenance therapy was associated with significantly longer overall and relapse-free survival than placebo among older patients with AML who were in remission after chemotherapy. CC-486 was approved in the

US and Canada in September 2020 and January 2021, respectively, and is indicated for continued treatment of adult patients with AML who achieved first CR/CRI following intensive induction chemotherapy and are not able to complete intensive curative therapy²⁸. An oral formulation of azacitidine (CC-486) has been developed and is currently being evaluated in clinical trials, either as a single agent or in combination with other drugs, for the treatment of hematological and solid malignancies. This oral formulation of azacitidine provides an opportunity for administration in a more convenient outpatient setting rather than in the hospital/clinic setting. Home administration also alleviates the morbidity of injection and catheter-site reactions and avoids the inconvenience and resource utilization costs associated with frequent hospital/clinic visits.

Results from the ongoing Phase 3, randomized, double-blind, placebo-controlled QUAZAR Study (CC-486-AML-001), which enrolled de novo AML and secondary AML participants, have shown that CC-486 (300 mg/day for 14 days of 28-day treatment cycles) as first-line maintenance therapy demonstrated significant and clinically meaningful improvement in OS and relapse-free survival (RFS) in AML in remission following induction chemotherapy with or without consolidation. Median follow-up was 41.2 months. Median OS was 24.7 months with CC-486 versus 14.8 months with placebo (P=0.0009; HR 0.69 [95% CI 0.55, 0.86]). Median RFS was 10.2 months in the CC-486 arm compared to placebo at 4.8 months (P=0.0001; HR 0.65 [95% CI 0.52, 0.81])²⁹. The RFS rate at the 6-month time point was 67.4% in the CC-486 group and 45.2% in the placebo group, for a difference of 22.2%. The RFS rates were consistently higher for the CC-486 group than for the placebo group at each of the later time points (44.9% versus 27.4% at the 1-year time point and 26.6% versus 17.4% at the 2-year time point, respectively).

3.3 Benefit/Risk Assessment

More detailed information about the known and expected benefits and risks and reasonably anticipated adverse events (AEs) of CC-486 may be found in the Investigator's Brochure (IB).

3.3.1 Risk Assessment

Table 3.3.1-1: Risk Assessment

Potential Risk of Clinical Significance	Summary of Data/Rationale for Risk	Mitigation Strategy
Study Intervention(s)		
Known/potential safety risks	
The known side effects associated with azacitidine treatment as very common (a 10% or more chance that this will happen) are:
 
anemia, neutropenia, leukopenia, febrile neutropenia, thrombocytopenia, bronchitis, cellulitis, pneumonia, oral fungal infection, skin infection, respiratory tract infection, upper respiratory tract infection, urinary tract infection, nausea, vomiting, diarrhea,
	
Patients should be monitored closely and appropriate actions taken following recommendations in Section 7.4.1.

Table 3.3.1-1: Risk Assessment

Potential Risk of Clinical Significance	Summary of Data/Rationale for Risk	Mitigation Strategy
	abdominal pain, upper abdominal pain, abdominal discomfort, constipation, asthenia, fatigue, malaise, pyrexia, nasopharyngitis, pharyngitis, laryngeal pain, decreased appetite, weight decreased, hypokalemia, arthralgia, back pain, bone pain, myalgia, musculoskeletal pain, pain in extremity, chest pain, dizziness, headache, insomnia, dyspnea, dyspnea exertional, rash, skin lesion, pruritus, ecchymosis, hematoma, petechiae, and epistaxis.	
Study Procedures		
Study design	Lower dose may not be able to show the comparable results with AML-001 study in spite of consistently observed equivalent exposure of 200 mg in Japanese participants as 300 mg in Caucasian participants.	Although the feasible number of subjects is limited, subjects are enrolled as many as possible. And evaluate comprehensively that the results of not only the primary endpoint but also the secondary endpoints and safety are at least not substantially inconsistent with the results of AML-001 study and also assess in detail the efficacy and safety for individual subjects.
Study design	Small sample size may not be able to show the comparable results with AML-001 study.	Although the feasible number of subjects is limited, subjects are enrolled as many as possible. And evaluate comprehensively that the results of not only the primary endpoint but also the secondary endpoints and safety are at least not substantially inconsistent with the results of AML-001 study and also assess in detail the efficacy and safety for individual subjects.
Study execution	
It may take time to enroll the target population for the following reasons:
 
 • anticipated limited number of patients who are fit for intensive chemotherapy but not allogeneic SCT (such intensive chemotherapy is for patients who are usually fit for allogeneic SCT as well) • setting a placebo-control arm 	
 • Carefully choose the study sites with high motivation to join this study and have recently shown good performance in hematologic malignancy studies. • Disseminate messages of CC-486-AML-001 study results as much as possible to encourage investigators and participants for this study.

Abbreviations: mRFS, median relapse-free survival; SCT, stem cell transplantation

3.3.2 **Benefit Assessment**

Benefit considerations may include:

- Prolongation of RFS in the maintenance setting of CC-486 compared with BSC.
- Contribution to provide actual evidence in Japanese participants with AML in complete remission (ie, whether similar benefit can be expected in Japanese participants).

3.3.3 **Overall Benefit/Risk Conclusion**

Taking into account the measures taken to minimize risk to participants in this study, the potential risks identified in association with CC-486 are justified by the anticipated benefits that may be afforded to participants with AML.

The Sponsor will evaluate the risk/benefit profile of the study on an ongoing basis. This evaluation will be based on all available data – with particular attention to AEs or other safety trends in this or any other clinical study of CC-486 whose character, severity, and/or frequency suggest that participants would be exposed to an unreasonable and significant risk of illness or injury.

If such evaluation suggests that the risk/benefit profile of the study has become unfavorable to participants, the Sponsor will pause enrollment and/or treatment until further evaluation of data, and interaction with the appropriate health authority(ies) can take place on potential actions. Such actions may include (but are not limited to) study continuation, substantial amendment, or termination of the study.

4 OBJECTIVES AND ENDPOINTS

Table 4-1: Objectives and Endpoints

Objectives	Endpoints	Estimands
Primary Objective	Primary Endpoint	Primary Estimand

• To evaluate the efficacy of CC-486 as maintenance therapy by using RFS in Japanese participants \geq 55 years with AML who have achieved first CR or CRI after induction with intensive chemotherapy with or without consolidation chemotherapy.	
• RFS	
• Population: All randomized Japanese participants \geq 55 years with AML, who have achieved first CR or CRI after induction with intensive chemotherapy with or without consolidation chemotherapy.• Treatment: CC-486 +/- BSC vs placebo +/- BSC as randomized• Intercurrent events: Participants without documented relapse at the time of study closure and participants who are withdrawn for any reason or start subsequent therapy will be censored.• Summary statistics: Kaplan-Meier curves, and hazard ratios from Cox

Table 4-1: Objectives and Endpoints

Objectives	Endpoints	Estimands
Secondary 
 • To determine the effect of CC-486 as maintenance therapy on OS, time to relapse from CR/CRi, and time to discontinuation from treatment • To determine safety and tolerability • To determine PK • To determine the effect of oral azacitidine on HRQoL 	Secondary 
 • OS • Time to relapse from CR/CRi • Time to discontinuation from treatment • Safety/tolerability (type, frequency, severity, and relationship of AEs to study treatments; physical examinations, vital signs; clinical laboratory evaluations, and concomitant medication/therapy) • PK parameters • Participant-reported outcomes utilizing the FACIT-Fatigue Scale and the EQ-5D-5L 	proportional hazards model with confidence interval. 
 • Population: 
 • OS, time to relapse from CR/CRi, time to discontinuation from treatment, and HRQoL: All randomized Japanese participants \geq 55 years with AML who have achieved first CR or CRi after induction with intensive chemotherapy with or without consolidation chemotherapy. • Safety/tolerability: All treated participants • PK parameters: All participants with PK sampling with CC-486 treatment • Treatment: 
 • OS, time to relapse from CR/CRi, time to discontinuation from treatment, safety/tolerability, and HRQoL: CC-486 +/- BSC vs placebo +/- BSC as randomized • PK parameters: CC-486 +/- BSC • Intercurrent events: 
 • OS: Lost to follow-up or all other intercurrent events • Time to relapse from CR/CRi: Death or start of subsequent therapy • Time to discontinuation from treatment: Relapse, death, or start of subsequent therapy • Safety/tolerability, PK parameters and HRQoL: All intercurrent events (eg, start of subsequent therapy) will be handled with treatment policy (ie, use information after intercurrent event) • Summary statistics: 
 • OS, time to relapse from CR/CRi, and time to discontinuation from treatment: hazard ratio from Cox proportional hazards model with confidence interval

Table 4-1: Objectives and Endpoints

Objectives	Endpoints	Estimands
		
 Safety/tolerability: Proportion of patients with event within treatment arms PK parameters: PK parameters in CC-486 arm HRQoL: Difference of HRQoL change from baseline scores within treatment arms
Exploratory 
 To determine plasma concentration of azacitidine and explore exposure-response relationships of efficacy and safety endpoints To determine cytogenetic status as indicator of pending AML relapse To evaluate molecular and/or cellular markers in the blood and bone marrow post induction and during maintenance therapy that may be predictive of clinical outcomes with oral azacitidine, including OS and RFS, following CR/CRi 	Exploratory 
 Correlative analyses to assess the relationships between azacitidine exposure and safety, efficacy, and exploratory pharmacodynamic endpoints (eg, DNA methylation) Analysis of genetic alterations, including gene sequencing for recurrent gene aberrations in AML Flow cytometric analysis of hematopoietic cell immunophenotypes - MRD 	

Abbreviations: AE, adverse event; AML, acute myeloid leukemia; BSC, best supportive care; CR, complete remission; CRi, complete remission with incomplete blood count recovery; DNA, deoxyribonucleic acid; EQ-5D-5L, EuroQol 5-dimension 5-level questionnaire; FACIT, Functional Assessment of Chronic Illness Therapy; HRQoL, health-related quality of life; IgG, immunoglobulin G; MRD, minimal residual disease; OS, overall survival; PK, pharmacokinetic(s); RFS, relapse-free survival.

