- Candidate for allogeneic bone marrow or stem cell transplant at screening.
- Have achieved CR/CRI following therapy with hypomethylating agents
- Received therapy with hypomethylating agents for MDS and went on to develop AML within four months of discontinuing the therapy with hypomethylating agents.

Intervention Groups and Duration:

Total duration of study participation for each participant: screening phase for 4 weeks, treatment phase until AML relapse, and follow-up phase until death, withdrawal of consent, study termination, or loss to follow-up.

Dose regimen: 200 mg once daily of CC-486 or placebo will be taken for the first 14 days of each 28-day treatment cycle.

Dose modification for toxicity and dose/schedule adjustment with AML relapse are allowed.

Study Intervention:

Study Intervention for CA055005		
Medication	Potency	IP/Non-IP/AxMP
CC-486	150mg/200mg	IP
Placebo	150mg/200mg	IP

Abbreviations: AxMP, auxiliary medicinal product; IP, Investigational Product.

Statistical Methods:

The primary efficacy analysis will be conducted for the Intent-to-Treat Population and will compare the RFS distributions between the two treatment groups. A Cox proportional hazards model will be used to estimate the corresponding hazard ratio and 95% CI for CC-486 relative to placebo. The RFS curves will be estimated using Kaplan-Meier methods.

Data Monitoring Committee: No

A Data Monitoring Committee or other review committee will not be used in the study.

Other Committee: No

Other review committee will not be used in the study.

Brief Summary:

CA055-005 is designed as a 2:1 randomization of CC-486 or placebo to assess the efficacy and safety of maintenance treatment with oral azacitidine in a cohort of Japanese participants ≥ 55 years with AML, and in CR/CRi after intensive induction chemotherapy with or without consolidation chemotherapy. The primary endpoint of RFS and the secondary endpoints of OS, safety, PK, and HRQoL will be evaluated and allow for a comprehensive investigation of efficacy, exposure/safety, and appropriateness of the clinical recommended dose for the Japanese population in comparison with the data from Study CC-486-AML-001.

Study Duration: 3 years

Study Intervention Duration: Until AML relapse in each participant.

Study Visit Frequency: On Days 1, 8, 15 and 22 in Cycles 1 and 2, Days 1 and 15 in Cycles 3 through 24, and Day 1 in Cycle 25 and beyond.

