8 DISCONTINUATION CRITERIA

8.1 Discontinuation From Study Intervention

Participants MUST discontinue IP (and Non-IP/AxMP at the discretion of the investigator) for any of the following reasons:

- Disease relapse

Participants will be discontinued from treatment when they meet the following criteria:

- Appearance of > 15% blasts in the bone marrow or peripheral blood
- The above occurrence should be attributed to relapse following CR/CRi, and not attributable to any other cause (eg, bone marrow regeneration after consolidation therapy or myeloid growth factor administration).

- Participant's request to stop study intervention. Participants who request to discontinue study intervention will remain in the study and must continue to be followed for protocol-specified follow-up procedures. The only exception to this is when a participant specifically withdraws consent for any further contact with him/her or persons previously authorized by the participant to provide this information
- Any clinical AE, laboratory abnormality, or intercurrent illness which, in the opinion of the investigator, indicates that continued participation in the study is not in the best interest of the participant
- Participant withdraws from active treatment but continues follow-up
- Participant becomes eligible (per Investigator) for allogeneic bone marrow or stem cell transplantation during the treatment period
- Death
- Loss to follow up
- Protocol violation
- Termination of the study by BMS
- Loss of ability to freely provide consent through imprisonment or involuntarily incarceration for treatment of either a psychiatric or physical (eg, infectious disease) illness. (Note: Under specific circumstances and only in countries where local regulations permit, a participant who has been imprisoned may be permitted to continue as a participant. Strict conditions apply, and BMS approval is required.)

Refer to the [Schedule of Activities](#) for data to be collected at the time of treatment discontinuation and follow-up and for any further evaluations that can be completed.

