Participants' reports of general health status will be assessed using the EQ-5D-5L questionnaire ([Appendix 9](#))³⁵. The EQ-5D-5L has 2 components: a descriptive system and a visual analog scale (VAS). The instrument's descriptive system consists of 5 dimensions: mobility, self-care, usual activities, pain/discomfort, and anxiety/depression. Each dimension describes 5 levels of problems, including "no," "slight," "moderate," "severe," and "extreme" or "unable to." A dimension for which there are no problems is said to be at level 1, while a dimension for which there are extreme problems is said to be at level 5. Thus, the numbers 11111 and 55555 represent the best health state and the worst health state, respectively, described by the EQ-5D-5L. Altogether, the instrument describes $5^5 = 3,125$ health states. Empirically, derived weights can be applied to an individual's responses to the EQ-5D-5L to generate a utility index measuring the value to society of his or her current health. In addition, a VAS allows respondents to rate their own current health on a 101-point scale ranging from 0 = "worst imaginable" to 100 = "best imaginable." The EQ-5D-5L takes approximately 5 minutes to complete.

9.2 *Adverse Events*

The definitions of an AE or SAE can be found in [Appendix 3](#).

AEs will be reported by the participant.

The investigator and any qualified designees are responsible for detecting, documenting, and reporting events that meet the definition of an AE or SAE and remain responsible for following up on AEs that are serious, considered related to the study intervention or the study, or that caused the participant to discontinue before completing the study.

Refer to Appendix 3 for SAE reporting.

9.2.1 *Time Period and Frequency for Collecting AE and SAE Information*

All SAEs and non-serious AEs must be collected from the time of signing the consent, including those thought to be associated with protocol-specified procedures, and within 28 days following discontinuation of dosing or until the End of Treatment Visit, whichever is later.

The investigator must report any SAE that occurs after these time periods and that is believed to be related to study intervention or protocol-specified procedure.

- Medical occurrences that begin before the start of study intervention but after obtaining informed consent will be recorded on the appropriate section of the CRF module.

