10 STATISTICAL CONSIDERATIONS

10.1 Statistical Hypotheses

The primary endpoint is RFS. Based on the median RFS in the CC-486 and placebo groups of Study CC-486-AML-001, the expected median RFS was set at 4.8 months for placebo, and the expected median RFS was set at 9.5 months for CC-486.

As the primary efficacy analysis, a Cox proportional hazards model will be used to estimate the corresponding hazard ratio and 95% CI for CC-486 relative to placebo. RFS curves will be estimated using Kaplan-Meier (KM) methods. The primary objective of this study is to estimate the efficacy of CC-486 as maintenance therapy by using RFS. The study does not plan to conduct any formal statistical hypothetical testing. For participants who do not have an RFS event, their RFS time will be censored at the last contact date (or "last known RFS date"). RFS will be censored at the date of randomization for participants who were randomized but had no response assessment.

Analysis of the primary endpoint will be conducted when the last subject completes 12 months follow-up. However, it may need to be reconsidered depending on the occurrence status of the event.

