10.4.3 Secondary Endpoint(s)

Overall Survival

The secondary efficacy endpoint of OS is defined as the time from randomization to death from any cause and will be calculated using the randomization date and date of death, or date of last follow-up for censored participants. All participants will be followed until dropout, death, or study termination. Participants who dropout or are alive at study termination will have their OS times censored at the time of last contact, as appropriate. OS analysis will be conducted for the ITT population.

Safety

All safety analyses will be performed on the Safety Population. Adverse events will be coded using the Medical Dictionary for Regulatory Activities (MedDRA). Adverse event listings will include the verbatim term and the MedDRA preferred term. Treatment-emergent adverse events (TEAEs) will be summarized by worst severity grade, system organ class, and preferred term. Treatment-emergent AEs leading to death or to discontinuation from treatment, AEs classified as NCI-CTCAE (Version 5.0) Grade 3 or Grade 4, AEs related to IP, and SAEs will be summarized separately. Time to discontinuation from the study due to AE will be summarized using KM methods. Listings of all deaths and all SAEs, regardless of when they occurred, will also be generated.

Pharmacokinetics

The sparse concentration-time data collected in this study may be combined with a larger dataset to help further develop and validate the population pharmacokinetic model for azacitidine and to aid in the identification of covariates that influence azacitidine pharmacokinetic and/or pharmacodynamic measures and efficacy and safety endpoints. PK population will be used for PK analysis. Noncompartmental analysis will be performed using intensive sampling data.

Health-related Quality of Life

PRO endpoints include FACIT-Fatigue and the EQ-5D-5L, and analyses will include the Health-related Quality of Life population. Summary statistics (N, mean with SD and 95% CI, median, first and third quartiles, minimum, maximum) for PRO measures at each assessment point will be provided for each treatment arm. The mean change from baseline will also be reported at each post-baseline assessment point. Additionally, for the EQ-5D-5L, the proportion of participants endorsing each response option will be calculated at each time point.

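### Adverse events are summarised as crude proportions with no exposure-adjusted or common-window incidence, although the plan expects CC-486 patients to be treated, and so observed for AEs, for longer than placebo patients

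*Combined protocol and SAP*

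**What the plan says.** For safety and tolerability, the estimand column of Table 4-1 gives the summary statistic as "Proportion of patients with event within treatment arms". Section 10.4.3 states: "Treatment-emergent adverse events (TEAEs) will be summarized by worst severity grade, system organ class, and preferred term". It also calls for separate summaries of selected AE classes and for listings of deaths and SAEs. Its one time-based safety item is: "Time to discontinuation from the study due to AE will be summarized using KM methods". Neither place mentions a person-time denominator, a time-to-first-AE analysis or AE incidence over a window common to both arms.

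The observation window depends on treatment. The Protocol Summary has "Study Intervention Duration: Until AML relapse in each participant", and Section 9.2.1 collects AEs "within 28 days following discontinuation of dosing or until the End of Treatment Visit, whichever is later". Section 10.1 states the planning medians: "the expected median RFS was set at 4.8 months for placebo" and "the expected median RFS was set at 9.5 months for CC-486".

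**The concern.** A crude proportion answers how many patients had the event while they were being watched. If one arm is watched longer, it accumulates more first events at the same underlying rate. Here the arm expected to be watched longer is the active one, and it is watched longer because the drug is expected to delay relapse. Part of any CC-486 excess in the AE tables could therefore reflect duration of benefit and not toxicity.

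The within-arm label does not prevent a comparative reading. The title says the study compares safety, and Section 3.1 uses exposure and safety to judge whether the dose suits Japanese patients. The treatment-policy handling in Table 4-1 does not equalise the windows, because routine AE collection stops soon after dosing does.

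**Working it through.** **Inputs.** Median RFS 4.8 and 9.5 months (Section 10.1); about 5 placebo and 10 CC-486 patients (Section 5.1); 28-day post-dose window, 0.92 month (Section 9.2.1); analysis when the last subject reaches 12 months (Section 10.1); study duration 3 years (Protocol Summary). The plan gives no expected time on treatment, AE rate or accrual period. These are assumed below.

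**The plan's own figure.** There is none for exposure or AEs. The figure that depends on the same medians is the 87% probability in Section 10.2 that the estimated hazard ratio is below 1. With HR = 4.8/9.5 = 0.505, 2:1 allocation and d events, the probability is Φ(|ln HR| × √(2d/9)). At d = 12 this is Φ(0.683 × 1.633) = 86.75%. With 12 to 24 months of assumed accrual it is 86.6% to 87.5%. The figure reproduces, so the two medians are working planning assumptions.

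**Exposure.** Take time on treatment as exponential with the RFS medians. The stopping hazards are h = ln 2/4.8 = 0.1444 and ln 2/9.5 = 0.0730 per month. Mean time up to a cut T is (1 − e^(−hT))/h:

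| Cut | Placebo | CC-486 | Ratio |
|---|---|---|---|
| 12 months | 5.70 | 8.00 | 1.40 |
| 24 months | 6.71 | 11.33 | 1.69 |
| 36 months | 6.89 | 12.71 | 1.85 |

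Adding 0.92 month to each mean gives ratios of 1.35, 1.61 and 1.75. With no cut, the ratio is 9.5/4.8 = 1.98. A common non-relapse stopping hazard k (assumed) lowers that to (0.1444 + k)/(0.0730 + k), which is 1.77 at k = 0.02 and 1.58 at k = 0.05.

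**Crude proportions under equal toxicity.** Give both arms the same first-AE hazard λ, and add 0.92 month for patients who stop before the cut. The proportion with an event is

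1 − [h/(h+λ)] e^(−0.92λ) (1 − e^(−(h+λ)T)) − e^(−(h+λ)T).

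For λ = 0.05 and T = 36:
- placebo: 1 − 0.7428 × 0.9550 × 0.9991 − 0.0009 = 29.0%
- CC-486: 1 − 0.5934 × 0.9550 × 0.9880 − 0.0120 = 42.8%

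| λ per month | 12-month cut, placebo vs CC-486 | Ratio | 36-month cut, placebo vs CC-486 | Ratio |
|---|---|---|---|---|
| 0.02 | 11.9% vs 15.4% | 1.30 | 13.7% vs 22.1% | 1.61 |
| 0.05 | 26.2% vs 33.4% | 1.27 | 29.0% vs 42.8% | 1.47 |
| 0.10 | 43.7% vs 53.8% | 1.23 | 46.1% vs 61.4% | 1.33 |
| 0.20 | 64.1% vs 74.8% | 1.17 | 65.1% vs 77.8% | 1.19 |
| 0.50 | 85.8% vs 91.9% | 1.07 | 85.9% vs 92.0% | 1.07 |

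The true rate ratio is 1.0 in every row. First events divided by person-time at risk recover it: simulation at λ = 0.05 gives 0.0500 per patient-month in both arms.

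**Chance at this sample size.** Simulating 10 versus 5 patients with λ from 0.02 to 0.20 and the 36-month cut, the crude proportion is higher on CC-486 in about 59% to 65% of trials and lower in about 23% to 25%.

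**Where rates fail.** Suppose an AE occurs only in the first 28 days, with equal 40% risk in both arms and mean onset at 0.46 month. Crude proportions are then correctly equal. Person-time to first event is 0.6 × (mean window) + 0.4 × 0.46.
- 36-month cut: mean windows are 7.80 (placebo) and 13.57 (CC-486), so the rate ratio is 4.86/8.33 = 0.58.
- 12-month cut: mean windows are 6.46 and 8.53, so the rate ratio is 4.06/5.30 = 0.77.

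Rates alone would make CC-486 look safer than it is for early toxicity.

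**The case against.** **The proportion is not the only safety output.** This stands. There are worst-grade tables, the Kaplan-Meier item, and listings of deaths and SAEs at any time. Time to discontinuation from treatment is a secondary endpoint, and Table 3.3.1-1 promises individual-level assessment. A reader will see that treatment durations differ, but none of these outputs gives AE incidence on a comparable time base.

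**RFS is not time on treatment.** This stands too. The stopping criterion in Section 8.1 is "Appearance of > 15% blasts in the bone marrow or peripheral blood", whereas the IWG definition in Appendix 6 counts relapse from 5% marrow blasts, so treatment can continue past an RFS event. Patients also stop for AEs, transplant eligibility or by request. The AE window itself is worded differently across the document: the schedule tables and Section 8.1 allow a later last visit. A reader might infer from the medians that exposure differs two-fold by design, but the plan states no such figure.

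**Small, descriptive safety data.** One placebo patient is 20 percentage points, more than the largest gap in the table (about 15 points), and no hypothesis is tested. This limits the practical effect. It does not remove a bias that has the same sign in every scenario examined.

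**Detail is left to the SAP.** Section 10.4 defers technical detail to a separate SAP, which may add exposure adjustment. Nothing in the current text commits to it.

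**Comparison with Study CC-486-AML-001.** A reader might infer that CC-486 would also look falsely worse against that study. The documents do not support this. CC-486 is set against CC-486, with median RFS of 9.5 months expected here and 10.2 months there (Section 3.2). With no cut, λ/(λ+h) at 0.05 per month is 40.7% here and 42.4% there, a ratio of 0.96; at 0.02 and 0.10 the ratios are 0.95 and 0.97. The effect is small and in the other direction. Shorter follow-up here would lower the proportion further.

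**Conclusion.** The point holds as a gap in the safety reporting for the comparison with placebo. If RFS approximates time on treatment and the AE hazard is constant and equal between arms, crude proportions are expected to favour placebo by a ratio of about 1.2 to 1.3 (12-month cut) or 1.3 to 1.6 (36-month cut) at 0.02 to 0.10 events per month. The distortion is proportionally largest for uncommon events accruing throughout treatment. It is nearly absent for very frequent ones (about 1.07), and absent for AEs confined to a first cycle that both arms complete.

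This is a statement about expectation. In a single trial of 10 versus 5 patients, chance can hide or reverse it. It does not show that the safety conclusions would be wrong. It also does not follow that rates should replace proportions, since rates fail in the opposite direction for early toxicity.

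**What to change.** In Table 4-1 and Section 10.4.3, keep the proportions and add by arm:

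- treatment duration;
- first events per 100 patient-months at risk, with confidence intervals, for TEAEs, Grade 3-4 AEs and SAEs, with the time at risk defined once and aligned with one statement of the AE collection window;
- proportions over a common early window, such as the first cycles, fixed before unblinding.

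State that the crude proportions, rates and common-window proportions will be read together, and that rates alone will not be used for comparison. Dosing start and stop dates are already recorded under Section 7.6, so the cost is a few table columns. The rates rest on a roughly constant hazard, which should be noted beside them, and their intervals will be wide at this sample size. No design or clinical rule changes.
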